5.7 Criteria for Removal from Study

Participants will be removed from study upon death or withdrawal of consent. The reason for study removal and the date the participant was removed must be documented in the medical record and recorded in the study-specific case report form (CRF). Alternative care options will be discussed with the participant, if applicable.

CONFIDENTIAL

This document is confidential. Do not disclose or use except as authorized.

In the event of unusual or life-threatening complications, participating investigators must immediately notify the Principal Investigator [name] at [REDACTED]

6. EXPECTED TOXICITIES AND DOSING DELAYS/DOSE MODIFICATIONS

6.1 Potential Toxicity

Radiation side effects are typically divided into those that occur acutely (during radiation and up to 3 months after radiation) and those that occur later (>3 months post-radiation). Common acute radiation side effects include fatigue, skin irritation or erythema, elevated liver function tests, nausea, low platelet count, decreased blood counts, abdominal pain or cramps, decreased/ loss of appetite, vomiting, slow wound healing, weight loss, indigestion, gastritis, radiation esophagitis, and diarrhea. Typically, these side effects can be controlled with medication.

Late side effects that are unlikely to occur but would include rib microfracture, nerve damage, inflammation and scarring of liver, mucosal ulceration and tissue damage, ulceration or perforation of stomach/ bowel, pain, inflammation, or scarring of kidneys, stomach and bowel, development of new cancer, hepatic injury (hepatitis), renal injury, gastric, bowel obstruction and spinal cord injury. Another rare but serious late side effect is the development of second tumors. It is hoped that proton radiation will substantially reduce both acute and late side effects by reducing the amount of normal tissue that is irradiated.

Dose delays and modifications will be made using the following recommendations. Toxicity assessments will be done using NCI Common Terminology Criteria for Adverse Events (CTCAE v3.0) which is available at <http://ctep.cancer.gov/reporting//ctc.html>).

If possible, symptoms should be managed symptomatically. In the case of toxicity, appropriate medical treatment should be used (including anti-emetics, anti-diarrheals, etc.).

All toxicities that are Grade 2 or higher and determined to be possibly, probably or definitely related to the study intervention or study procedures will be collected on the Toxicity case report forms from the time of the first dose of study treatment, through the study and until the final study visit. Participants continuing to experience toxicity at the off study visit may be contacted for additional assessments until the toxicity has resolved or is deemed irreversible.

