5.1.2 Radiation Therapy

5.1.2.1 Pre-planning and Simulation Procedures

Prior to radiation planning, patients will undergo placement of fiducial seeds according to institutional procedures. If placement of fiducials is contraindicated in a patient, or if a patient is deemed too high risk for implanting procedure, the patient may proceed with study participation without fiducials at the discretion of the treating investigator.

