11.1 General

Adverse event collection and reporting is a routine part of every clinical trial. This study will use the descriptions and grading scales found in the NCI Common Terminology Criteria for Adverse Events version 3.0 (CTCAE v3.0) that is available at <http://ctep.cancer.gov/reporting/ctc.html>

Information on all adverse events, whether reported by the participant, directly observed, or detected by physical examination, laboratory test or other means, will be collected, recorded, followed and reported as described in the following sections.

Adverse events experienced by participants will be collected and reported from initiation of study intervention, throughout the study, and within 30 days of the last study treatment. Participants who experience an ongoing adverse event or related to a study procedure and/or study treatment beyond 30

CONFIDENTIAL

This document is confidential. Do not disclose or use except as authorized.

days will continue to be contacted by a member of the study team until the event is resolved, stabilized, or determined to be irreversible by the participating investigator.

Participants should be instructed to report any serious post-study event(s) that might reasonably be related to participation in this study. The investigator should notify the IRB, the Coordinating Center and any other applicable regulatory agency of any unanticipated death or adverse event occurring after a participant has discontinued or terminated study participation that may reasonably be related to the study.

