11.2 Definitions

11.2.1 Adverse Event (AE)

An adverse event is any undesirable sign, symptom or medical condition or experience that develops or worsens in severity after starting the first dose of study treatment or any procedure specified in the protocol, even if the event is not considered to be related to the study.

Abnormal laboratory values or diagnostic test results constitute adverse events only if they induce clinical signs or symptoms or require treatment or further diagnostic tests.

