11.5 Coordinating Center Notification by Investigator

11.5.1 Serious Adverse Event Reporting Requirements

All events meeting the criteria for Serious Adverse Event (see Section 11.2.2) that occur after the initial dose of study treatment, during treatment, or within 30 days of the last dose of treatment must be reported to the DF/HCC Overall Principal Investigator as serious adverse events. This includes events meeting criteria outlined in Section 11.2 as well as the following:

- Grade 2 (moderate) and Grade 3 (severe) events that are unexpected and at least possibly related/associated with the intervention.
- All Grade 4 (life-threatening or disabling) events that are unexpected or not specifically listed in the protocol as not requiring reporting
- All Grade 5 (fatal) events while the participant is enrolled and actively participating in the trial OR when the event occurs within 30 days of the last study intervention.

Note: If the participant is in long-term follow-up, report death at the time of continuing review.

CONFIDENTIAL

This document is confidential. Do not disclose or use except as authorized.

The participating investigator must report each serious adverse event, regardless attribution, to the DF/HCC Principal Investigator within 1 business day of learning of the occurrence. In the event that the participating investigator does not become aware of the serious adverse event immediately (e.g., participant sought treatment elsewhere), the participating investigator is to report the event within 1 business day after learning of it and document the time of his or her first awareness of the adverse event. Report serious adverse events by email or fax to the Coordinating Center at:

Within the following 1-2 business days, the participating investigator must provide follow-up information on the serious adverse event. Follow-up information should describe whether the event has resolved or continues, if and how the event was treated, and whether the participant will continue or discontinue study participation.

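### The Toxicity form and the expedited SAE duty start at the first proton dose, after the default fiducial implant, although the protocol's own adverse event definition starts at any protocol procedure

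*Combined protocol and SAP*

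**What the plan says.** The treatment plan includes an invasive step before radiation. Section 5.1.2.1 states: "Prior to radiation planning, patients will undergo placement of fiducial seeds according to institutional procedures". Leaving it out is the exception, at the treating investigator's discretion, where it is contraindicated or the patient is judged too high risk for it.

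Section 11.2.1 defines an adverse event as one that "develops or worsens in severity after starting the first dose of study treatment or any procedure specified in the protocol", whether or not it is thought related to the study.

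Three sections say when collection or reporting begins:

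- **Section 6.1 (Toxicity case report form).** It covers toxicities of grade 2 or higher that are "possibly, probably or definitely related to the study intervention or study procedures". These "will be collected on the Toxicity case report forms from the time of the first dose of study treatment, through the study".
- **Section 11.1 (adverse events in general).** "Adverse events experienced by participants will be collected and reported from initiation of study intervention". The protocol does not define the starting event.
- **Section 11.5.1 (SAEs to the overall principal investigator, within 1 business day).** It covers events "that occur after the initial dose of study treatment, during treatment, or within 30 days of the last dose of treatment must be reported".

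**The concern.** The definition of an adverse event and the rules for collecting one start at different times, and an invasive liver procedure falls in between. Section 6.1 is also at odds with itself: it brings procedure-related toxicities into scope, then starts the clock after the implant has been done.

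Secondary objective 1.3.1 is the safety and tolerance of the treatment program, not only of the proton dose. Eligibility admits patients with platelets as low as 25,000/mcL (3.1.7) and Child-Pugh class B cirrhosis (3.1.8). Fiducials are placed by each center's own procedures at three proton centers, so a pattern of complications would show most readily in pooled data. The toxicity lists in 6.1 and 6.2 name no implant-specific risk. Such an event could therefore count as unexpected under 11.2.3.2, unless the consent form, which is not in the supplied text, lists it. Under 12.2, what the Data and Safety Monitoring Committee may receive includes unexpected events of grade 2 or higher that have been reported. An event that no window obliges a site to report may not reach the committee.

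**Working it through.** No arithmetic applies, and the plan states no figure to reproduce. The check sets the time points side by side.

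**Order of events.** Consent comes before any study procedure (4.2). The implant comes before radiation planning (5.1.2.1), and planning comes before the first fraction. The implant, where done, therefore always precedes the first dose.

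**Where each rule starts, relative to the implant.**

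| Section | Starts at | Covers the interval from implant to first fraction? |
|---|---|---|
| 11.2.1 definition | first dose or any protocol procedure | Yes |
| 6.1 Toxicity form | first dose | No |
| 11.5.1 expedited SAE report | after the initial dose | No |
| 11.1 general collection | start of study intervention, undefined | Unclear |

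**What follows for a complication of the implant.**

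1. *It resolves before the first fraction.* It is an adverse event under 11.2.1, but neither 6.1 nor 11.5.1 requires it.
2. *It prevents the first fraction.* The start point of 6.1 and 11.5.1 never occurs. For this patient 4.1 requires a change of protocol status, and separately says that issues causing treatment delays should be discussed with the principal investigator.
3. *It is still present at the first fraction, or worsens after it.* It can be recorded at the assessments during radiation, so it is not necessarily lost.
4. *It is fatal.* The grade 5 item in 11.5.1 covers deaths while a participant is enrolled and actively participating, which could bring it in.

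The gap is thus in cases 1 and 2.

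**Scheduled assessments.** The calendar in 9.1 has a toxicity assessment before study entry, at weekly visits during radiation, and at follow-up. None is tied to the implant or to the interval between entry and the first fraction.

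**Length of the interval.** Section 4.1 requires treatment to start within 1 month of registration. That does not bound the time from implant to first fraction, because no section says whether the implant comes before or after registration. If it comes after, the interval is at most about 1 month. If it comes after consent but before registration, the interval could be longer, though the pre-entry assessment might then note a complication.

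**The case against.** The strongest reply is that other duties carry no first-dose start. The opening of section 11 sends all adverse events to the Coordinating Center and all participating sites. Section 11.3 has adverse event information obtained at each contact and all events recorded on case report forms. Section 11.6 requires reports to the principal investigator and the local IRB, and 11.7 covers safety reports and sentinel events required by institutional policy. Section 5.7 requires immediate notice of unusual or life-threatening complications, and 4.1 brings treatment delays to the principal investigator. This stands as far as it goes. A reader might infer that implant complications go uncaptured and that nobody outside the site would learn of them; the documents do not support that. But none of these duties sets an explicit earlier start for the Toxicity form or the 1-business-day report, so sites could justify different practice.

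Other replies also have force:

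- Section 11.1 can be read to include the implant, which sits under the treatment program in section 5.1. The mismatch is firm for two windows, not three.
- The opening of section 11, 11.4 and 13.8 refer to the Data and Safety Monitoring Plan. It is not in the supplied text and may set another window. The protocol body would still disagree with itself.
- Section 10.1 defines the toxicity measure as morbidity of radiation treatment, and 14.4 analyzes it as so defined. Starting at the first dose suits that measure. It would be wrong to infer that the planned radiation toxicity rates are in error.
- High-risk patients may skip the implant, and these may include the patients with the lowest platelet counts, so the exposed group is smaller than the whole trial.

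**Conclusion.** The point holds as an internal contradiction with a limited consequence. Sections 6.1 and 11.5.1 open later than the definition in 11.2.1 and later than the default implant in 5.1.2.1, and 11.1 is ambiguous. Implant complications that resolve before the first fraction, or prevent it, need not be entered on the Toxicity form or reported as SAEs within 1 business day.

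The size cannot be given as a number. The documents state no implant complication rate, no count of patients expected to have fiducials, and no expected number of serious events. A reader might be tempted to apply an assumed rate to all 90 planned patients and call the result events missed. That would ignore patients who skip the implant, complications that continue into radiation, and events caught by the general duties.

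What is affected is the completeness and consistency of safety data under objective 1.3.1. The primary test of 2-year local control is unaffected. The conclusion assumes that the Data and Safety Monitoring Plan does not already set an earlier start. If it does, the protocol text still needs to be brought into line with it.

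**What to change.** - In 6.1, 11.1 and 11.5.1, start collection and SAE reporting at the first protocol-specified procedure, naming fiducial placement, so that all three match 11.2.1. Check the Data and Safety Monitoring Plan for the same wording.
- Define study intervention, so that 11.1 has one reading.
- Tabulate procedure-related events for all registered patients who had the implant, including those who never start protons. Keep this table apart from the radiation toxicity rates of 10.1 and 14.4, so that those rates retain their meaning.

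The cost is a wording amendment in three places, a change to the start-date logic of the case report form, a few more events to record, and a slightly less favorable safety summary. No dose or clinical rule changes.

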6.2 Anticipated Toxicities

CONFIDENTIAL

This document is confidential. Do not disclose or use except as authorized.

A list of the adverse events and potential risks associated with the agents administered in this study appear below and will determine whether dose delays and modifications will be made or whether the event requires expedited reporting **in addition** to routine reporting.

CAEPRs for Proton Beam Radiotherapy to the Liver

Very likely: These symptoms usually recover in the first few weeks following completion of radiation therapy

- Irritation, redness and discoloration of the skin in the radiation area.
- Fatigue (tiredness)

Likely

- Decreased blood counts
- Low platelet count
- Elevated LFTs
- Abdominal pain or cramps
- Nausea

Less likely

- Diarrhea
- Decreased/ loss of appetite
- Vomiting
- Slow wound healing
- Weight loss
- Indigestion
- Gastritis
- Radiation Esophagitis
- Rib microfracture

Rare

- Damage to the liver which could result in inflammation and scarring of the liver. This could lead to jaundice and possibly cirrhosis. Efforts to prevent excessive liver irradiation will be made to minimize the chance of these side effects
- While radiation can cause mucosal ulceration, other tissues may be damaged which may require surgery and may be life-threatening.
- Stomach and bowel are protected well from excessive dose of radiation. However, overdosing the stomach or bowel can lead to ulceration or perforation.

CONFIDENTIAL

This document is confidential. Do not disclose or use except as authorized.

- Pain, inflammation or scarring of your kidneys, stomach and bowel. These organs are protected well from excessive dose of radiation. Therefore, it is unlikely that patients will experience symptoms of injury to these organs
- Nerve damage
- Development of a new cancer resulting from treatment may happen many years after completing treatment
- Spinal cord injury

6.3 Toxicity Management

Most radiation toxicities during the course of treatment are self-limited and resolve with a treatment break. Therefore, any Grade 3 or 4 acute toxicity will result in a treatment break until it resolves to Grade 2 or less, with the exception of labs. All labs will be assessed by the treating physician to determine whether they are considered clinically significant or not clinically significant and treatment will be held at their discretion. If a participant experiences a Grade 3 or 4 hematological toxicity, the participant is allowed to receive a colony stimulating factor to aid in the resolution.

6.4 Dose Modifications/Delays

Grade 3 or 4 acute toxicity will result in a treatment break until it resolves to Grade 2 or less, with the exception of any Grade 3 Baseline labs that fit the eligibility criteria. Thrombocytopenia will only result in a treatment break if it becomes a Grade 4. All labs will be assessed by the treating physician to determine whether they are considered clinically significant or not clinically significant and treatment will be held at their discretion. If a treatment break of > 14 days is needed, the patient will be removed from study.

7. DRUG FORMULATION AND ADMINISTRATION: Not applicable

8. CORRELATIVE/SPECIAL STUDIES

8.1 Circulating Biomarkers

Participation in the correlative blood sample studies will be offered to study participants at MGH only.

Based on findings from preliminary studies, we propose here to evaluate the changes in blood circulating SDF1 α and circulating myeloid cells before, during, and after a three-week schedule of proton beam radiation therapy, and to explore potential associations between the changes in these biomarkers and resistance to treatment. In exploratory studies, we will evaluate several other cytokines using multiplex protein array (Meso-Scale Discovery, Inc.).

8.1.1 Experimental Design

CONFIDENTIAL

This document is confidential. Do not disclose or use except as authorized.

Blood will be drawn by venipuncture, and the first 7-10 ml blood will be excluded or used for other analysis. The following 8 ml will be collected in an EDTA tube. The EDTA tube with the blood sample will be shipped in wet ice within 2 hours of drawing for further processing at Steele Laboratory at MGH. We will analyze the correlation between plasma SDF1 α and circulating myeloid cells with multiple measures of outcome (ORR, TTP, OS) in advanced liver cancer patients after proton beam radiation therapy.

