Given these promising results in otherwise incurable malignancies, the MGH group undertook a Phase I study to evaluate the use of high dose conformal proton beam irradiation for selected patients with hepatocellular cancer, cholangiocarcinoma and hepatic metastases. The dose escalation was based on a model based on the amount of radiation that the normal liver received, or equivalent uniform dose (EUD) to the liver. The eligibility criteria were 1-3 lesions, greatest less than 6 cm in size, Childs A/B, and no extrahepatic disease. Patients were treated with gated proton beam therapy using 4D treatment planning techniques. Generally, patients have been treated to a dose of 45-75 Gy (RBE) in 15 fractions. The study was a dose escalation trial based on liver EUD. The dose that each patient was treated to was based not only on the liver EUD at each step but had to comply with protocol defined normal tissue constraints (bowel, chest wall). To date, there have been no local failures or radiation-induced liver disease through 3 of the first 4 dose levels.

CONFIDENTIAL

This document is confidential. Do not disclose or use except as authorized.

Because of the limitations of the EUD based liver concept as a dose escalation platform, as well as the non dose-limiting nature of liver with proton therapy, we have decided to proceed with a modification of the approach taken by the Tsukuba group (13). Investigators at Tsukuba have treated 165 patients (192 tumors) with a similar 15 fraction protocol to a median dose of 72 Gy. Patients with tumor sizes of 10 cm or greater were allowed on the study. Central tumors (within 2 cm of the porta hepatis) were treated to 66 Gy in 22 fractions because of concerns of toxicity. Local control at 5 years was an impressive 86.9%. Local control at 2 years was 90%. However 5 yr OS was only 23%, highlighting the out of field progression and comorbidities in these patients. In this study, we propose a treatment schedule of 15 fractions of proton beam radiation with an expected 2 yr LC of > 85%. Because we anticipate treating large tumors generally greater than 3 cm, we will seek to improve upon a RFA local control rate of ~ 50% to 80% with proton beam therapy.

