2.4 Correlative Studies Background

Preclinical and clinical work in the Steele Lab and elsewhere has identified the stromal-derived factor 1 alpha (SDF1 α) as an attractive candidate for biomarker of resistance to various therapies, but its role after proton beam radiation therapy is unknown. Based on findings from preliminary studies, we propose here to evaluate the changes in blood circulating SDF1 α and circulating myeloid cells before, during and after a three-week schedule of proton beam radiation therapy, and to explore potential associations between the changes in these biomarkers and resistance to treatment. In exploratory studies, we will evaluate several other cytokines using multiplex protein array (Meso-Scale Discovery, Inc.).

Circulating cell populations will be evaluated by fluorescence-based flow cytometry. Protein concentration in plasma will be measured using ELISA kits for SDF1 α and MSD multiplex kits for cytokines (IL-1, IL-6, IL-8 and TNF- α) vascular growth factors (VEGF, sVEGFR1, PlGF and bFGF). These techniques have been used in the Steele Lab for over 8 years to evaluate patients' samples.

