8.2 Genotype Testing

Next generation sequencing and tissue-based testing on specimens of patients at MGH will assess exploratory tissue markers in relation to worsening local control and will potentially inform future trials.

Next generation sequencing assays have been developed by the Massachusetts General Hospital Center for Integrated Diagnostics (MGH CID) to detect a wide variety of alterations in cancer genes that could alter response to therapy. The 1K Cancer Panel provides for the evaluation of small nucleotide variants (SNVs) and insertion/deletions (indels) across ~800 cancer genes using tumor DNA. The Solid Tumor Fusion Panel can detect gene fusions across ~50 gene targets using complimentary DNA (cDNA). Both of these approaches generate target-enriched libraries that undergo next-generation sequencing on an Illumina platform. A blood sample is used as a control to identify alterations that occur specifically in the tumor tissue. All testing and sequence analysis will be performed in the MGH Translational Research Laboratory (MGH TRL) within the MGH CID.

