14.1 Study Design/Endpoints

The primary endpoint is local control at 2 years, or equivalently, the absence of local failure as defined in 10.3. Starting with a total of 60 patients with unresectable primary hepatocellular cancer, we project 30 of them will be alive at 2 years for the evaluation of local control assuming a 2-year overall survival of 50%. The number of evaluable patients is a conservative assumption based on the historical RFA data and the Tsukuba proton data (13) showing a 2-year overall survival in the range of 50-70%. Analysis of 30 patients alive at 2 years will achieve 94% power to detect a local control rate of 80% if at least 21 of them were free of local failure. The decision rule is associated with 7% probability for accepting the proton protocol is associated with improved local control when the true rate is only 55% at 2 years.

The rate of local control will be based on actuarial estimates, primarily at 2 years, using the Kaplan-Meier method. Time to local failure will be measured from the start of radiation therapy to the date of local failure, as defined in 10.3. Patients who have not failed locally will be censored at the time of last follow-up. A minimum follow-up of 2 years will be required, while patients who die or drop out of the protocol prior to 2 years will be censored at that date.

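### The circulating-biomarker study asks about resistance to proton therapy but leaves local failure out of its outcomes

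*Combined protocol and SAP*

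**What the plan says.** Section 2.4 presents SDF1 alpha as a candidate resistance marker for several therapies and says that "its role after proton beam radiation therapy is unknown". Section 8.1 gives the aim: "to explore potential associations between the changes in these biomarkers and resistance to treatment". Section 8.1.1 names the outcomes for the circulating markers: it plans to correlate plasma SDF1 alpha and "circulating myeloid cells with multiple measures of outcome (ORR, TTP, OS").

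The tissue study in 8.2 uses a different outcome: it "will assess exploratory tissue markers in relation to worsening local control". Section 14.1 states: "The primary endpoint is local control at 2 years, or equivalently, the absence of local failure as defined in 10.3". None of sections 14.1 to 14.5 describes a biomarker analysis, so nothing there adds local failure to the list in 8.1.1.

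Section 2.3 comments on what drives survival. In the Japanese proton series local control was 90% at 2 years and 86.9% at 5 years. "However 5 yr OS was only 23%, highlighting the out of field progression and comorbidities in these patients". For the photon dose-escalation series, the same section attributes most deaths to advancing cirrhosis.

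**The concern.** Proton therapy acts within the irradiated volume, and the trial measures durable success there by freedom from local failure. A study of resistance to that treatment would be expected to relate the markers to that outcome. The protocol does so for tissue markers but not for blood markers.

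Two things are at stake. An association with OS or TTP could arise from liver function or disease elsewhere and be reported as a marker of proton resistance. Conversely, a marker that truly relates to local control could look weak because local failures are mixed with more frequent events of other kinds.

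**Working it through.** **1. The plan's own figures.** Section 8.1 gives no sample size, event count or power. The nearest design figure is the primary rule in 14.1 (at least 21 of 30 free of local failure). Exact binomial: P(X ≥ 21 | 0.80) = 0.9389 and P(X ≥ 21 | 0.55) = 0.0694. These reproduce the stated 94% and 7%. They concern the primary test only; the 80% rate is used below.

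**2. What each outcome captures, from section 10.**

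| Outcome | Treated lesion | Other content |
|---|---|---|
| ORR (10.2) | Yes: partial response is shrinkage of the primary lesion | Complete response also requires no other disease; measures shrinkage, not durable control |
| TTP (no entry in section 10) | Partly, if based on PD in 10.2 | PD also includes any new lesion |
| OS (10.7) | Only indirectly | Death from any cause |
| Local failure (10.3) | Yes | None; not listed in 8.1.1 |

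PD cannot stand in for local failure even in the treated lesion. PD is a 20% increase from the smallest recorded diameter, whereas 10.3 requires growth beyond the pre-treatment extent. As an illustration, a lesion going from 50 mm to 30 mm and back to 36 mm has grown by 6/30 = 20%, so it is PD, but it may lie wholly within its original extent. Time origins also differ: start of radiation for local failure (14.1), registration for OS (10.7), none stated for TTP.

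**3. Local failures relative to deaths.** Inputs: 2-year local control 80%; 2-year survival 50% as planned, within a historical range of 50-70% (all from 14.1). Assumption: constant, independent hazards, so hazard = −ln(2-year rate)/2.

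- Local failure: −ln(0.80)/2 = 0.1116 per year
- Death at 50% survival: −ln(0.50)/2 = 0.3466; share 0.1116/(0.1116 + 0.3466) = 0.244
- Death at 70% survival: −ln(0.70)/2 = 0.1783; share 0.1116/(0.1116 + 0.1783) = 0.385

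A marker that doubles only the local failure hazard would show a hazard ratio of 1 + share on this composite: 1.24 and 1.385. The plan names no such composite. It is used here only because both rates are in the documents.

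**4. OS.** The chance of local failure before death within 2 years is the share times (1 − 0.80 × survival).

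- 50% survival: 0.244 × 0.60 = 0.146, or 8.8 per 60 patients. Even if all of these patients died by 2 years, they would be 0.146/0.50 = 29% of deaths.
- 70% survival: 0.385 × 0.44 = 0.169; the same extreme bound is 0.169/0.30 = 56%.
- The 5-year figures in 2.3 (86.9% and 23%) give a bound of 9%.

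**5. TTP.** The documents give no progression rate. If 2-year freedom from progression is F, the local share is ln(local control)/ln(F). For assumed F from 20% to 60%, this is 14-44% at 80% local control and 7-21% at 90%. It exceeds half only when F exceeds 0.80² = 64%, or 0.90² = 81%.

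To illustrate dilution, take a median split and an assumed hazard ratio of 3 on local failure only. With a local share of 20%, the TTP hazard ratio is (0.8 + 3 × 0.1)/(0.8 + 0.1) = 1.22. With 40%, it is (0.6 + 3 × 0.2)/(0.6 + 0.2) = 1.50.

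**6. What adding local failure would deliver.** The number of MGH biomarker participants is not stated. With an assumed 20 to 60 patients and 10-20% local failure, there would be 2 to 12 events. Power for a hazard ratio of 3 (two-sided 0.05, median split) is Φ(√(d/4) × ln 3 − 1.96): 12% at d = 2 and 48% at d = 12. About 27 local failures would be needed for 80%.

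**The case against.** The strongest reply is that the chosen outcomes are defensible. The protocol speaks of resistance to treatment without limiting it to the irradiated volume, and for a blood-borne marker, overall response, progression and survival are reasonable exploratory outcomes. The study is optional, confined to one site and tied to no decision. Local failure is collected anyway, so it can be analysed later, and the counts in step 6 suggest that such an analysis would be imprecise. All of this stands and limits the weight of the point. It does not explain why 8.2 uses local control and 8.1.1 does not.

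A reader might infer that most events in the biomarker analysis say nothing about the treated lesion. The documents do not support that. ORR rests largely on the treated lesion, and PD includes growth of that lesion. Whether local events are a minority of TTP events depends on an unstated progression rate, and for deaths the extreme bound passes half at 70% survival.

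A reader might also take 24% as an upper limit. It belongs to the 50% end of the plan's survival range; the share is 38.5% at the other end.

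Nor is TTP wholly without definition: 10.2 defines PD and 14.4 gives Kaplan-Meier for time to failure. What is missing is an explicit event rule and a time origin.

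**Conclusion.** The point holds as a minor one. The aim in 8.1 concerns resistance to proton therapy, and 8.1.1 omits the plan's own time-to-event measure of control in the treated lesion. An effect specific to local control would be diluted in TTP and OS, while ORR would still carry some of it.

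The degree of dilution is not fixed by the documents. Local failures are about 24% to 38.5% of first local-failure-or-death events across the plan's 50-70% survival range. This assumes 80% local control, constant independent hazards, and that planning rates for hepatocellular cancer apply to the MGH participants, who may have either tumour type. Any figure for TTP rests on an assumed progression rate.

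The documents do not support saying that the listed outcomes are uninformative about the treated lesion, or that adding local failure would make the study well powered. The primary endpoint and its test are untouched.

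**What to change.** In 8.1.1:

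- Add time to local failure (10.3) as an exploratory outcome, analysed by cause-specific hazard. Censoring at death, as 14.1 already does, fits this.
- When the predictor is a change in a marker, count time from the later sample and include only patients still at risk then. A change to the one-month sample exists only for patients who reached it. The sample taken after radiologic progression is triggered by an outcome and should not be used as a predictor in this way.
- Keep ORR and OS. State the event rule and time origin for TTP, and report it by site of first failure using the categories in 10.3 to 10.6.

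The cost is analysis wording only. Local failure is already collected, and 5.6 provides for a 2-year local control analysis in patients who leave treatment or follow-up. The drawback is the small number of local failures at one site, so results should be given as estimates with intervals, which will be wide, and without a claim based on significance.
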